7.5.5 Electrocardiograms (ECGs)

Subjects with normal, not clinically significant abnormal, and clinically significant abnormal results as assessed by investigator for the 12 lead ECG will be listed.

7.5.6 Physical Exam

Any physical examination findings will be listed.

7.6 Interim Analysis

Safety data will be provided for DEC review after the sentinel subjects and after each dose cohort for the adult and elderly populations after the Day 7 visit for dose escalation decisions. Prior to initiating enrollment of the elderly subjects, the DEC will review the available data through 30 days post immunization in adult subjects. Details are provided in the DEC Charter.

The immunogenicity endpoint will occur 30 days after immunization. Once all subjects in Stage 1 have completed 30 days, there will be a database cut-off to conduct a formal analysis of the immunogenicity data. All data will be cleaned and the treatment assignment will be unblinded to Astellas. Treatment assignment will continue to be unavailable to the sites until after all subjects have completed the 180-day follow-up, all data has been cleaned and the database has been locked.

Similarly for subjects in Stage 2 once Stage 2 subjects have completed 30 days, there will be a database cut-off to conduct an interim analysis of the immunogenicity data. All data will be cleaned and the treatment assignment will be unblinded to Astellas. Treatment assignment will remain unavailable to the sites until after all subjects have completed the 180-day follow-up and the database has been locked.

In addition, there will be an expedited assessment of whether there is an immune response to ASP3772 in the Stage 1, adult subjects. The vendor responsible for analyzing the immunogenicity data will provide a file of the immunogenicity results with the patient numbers to an unblinded member of Bioanalytics team who will then add the treatment assignment and remove the subject numbers. The data will be sorted based on treatment assignment, which will further obscure the possibility of identifying the individual treatment assignment for an individual subject. Summaries of the IgG and OPA titers will be provided by ASP3772 dose and for combined Prevnar 13 subjects. The purpose of this exercise is to determine if any doses should be eliminated from the planned toddler study due to insufficient immunogenicity in the healthy adult population.

7.7 Handling of Missing Data, Outliers, Visit Windows, and Other Information

7.7.1 Clinical Laboratory (Hematology, Biochemistry, and Urinalysis) Analysis Windows

Analysis Visits	Scheduled Day in Protocol	Analysis Windows (day)
Baseline	Day 1	Last non-missing value between -28 and 1 (inclusive)
Visit 3	Day 7	Closest non-missing post immunization value to study day 7
Visit 4	Day 30	Closest non-missing post immunization value to study day 30

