5.4.7 Electrocardiogram

Standard 12-lead ECG recordings will be used for the purposes of safety assessment and subject management by the Investigator.

A 12-lead, resting ECG is to be recorded at each timepoint as indicated in Table 1, Table 2 and Table 3 (Schedule of Assessments). Subjects should remain supine for at least 5 minutes prior to all ECGs. Dates and times may be generated by the machine's internal clock and are considered source data. The results are to be interpreted by qualified personnel in real time for the management of the subjects' clinical condition. The principal investigator/designee will initial and date, and provide his/her clinical interpretation on each report. The results (normal, abnormal not clinically significant, abnormal clinically significant) are to be recorded in the electronic case report forms (eCRFs).

The ECG recorded during screening will be used to determine eligibility for study participation. Subjects who have a clinically significant abnormal ECG will not be eligible

for the study. The interpretation of the ECG from screening will be the baseline to which post-study vaccine dosing ECGs will be compared.

Unscheduled ECGs will be performed if clinically indicated.

If a machine-read corrected QT interval exceeds 500 msec after repeat measurement, this should be reported as an AE.

The original print-out and an electronic copy of all scheduled and unscheduled ECG tracings should be maintained on site as source data.

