- a. Screening will be completed up to 28 days prior to study immunization. Subjects will be assigned a subject number for use throughout the study at the screening visit via the Interactive Response Technology (IRT) system
- b. Informed consent must be obtained prior to the performance of any study-related procedure and before Randomization.
- c. Subjects will be randomized via the IRT at the dosing visit.
- d. Medical history will be collected at screening in order to assess Inclusion/Exclusion criteria and will be reconfirmed prior to study immunization.
- e. A physical examination will be performed at screening visit (days -28 thru -3), prior to study immunization (day 1) and day 30 visits.
- f. Perform tests for Hepatitis B surface antigen (HBsAg), hepatitis B core antibody (anti-HBc), hepatitis A virus antibodies (immunoglobulin M), HCV antibody (anti-HCV) confirmed by reflex testing (HCV-RNA) and HIV antigen/antibody (type 1 and/or type 2) at screening.
- g. Perform screening test for amphetamines, barbiturates, benzodiazepines, cannabinoids, cocaine and opiates at screening visit. Repeat urine drug screening before study immunization.
- h. Serum pregnancy test will be done at the screening visit. Urine pregnancy test will be done at study immunization (day 1) and day 30 visits. Not necessary for female subjects who are not of childbearing potential (e.g., post-menopausal [defined as at least 1 year without any menses] or documented surgically sterile) at screening and dosing visit.
- i. Body temperature, blood pressure and pulse rate will be assessed in a sitting position. At the dosing visit, body temperature, blood pressure, pulse rate and respiratory rate will be assessed predose and approximately 30 min and 1 hour postdose. Predose vital signs should be collected close to the vaccination and should not be more than 30 minutes prior to dose administration. Body temperature will be collected by the subject daily through day 7 following the study immunization.

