Physical Examination ^e	X	X†			X	
Routine 12-lead ECG	X	X†		X	X	
Virology ^f	X					
Height, Body Weight	X					
Study Immunization		X				
Vital Signs (blood pressure, pulse rate, body temperature) ^g	X	X†		X	X	
Clinical Laboratory Tests (hematology, biochemistry, coagulation profile, hepatic profile, urinalysis) ^h	X	X†‡		X	X	
CC1						
Serum sample for Immunogenicity ^j		X†			X	
Serum sample for Anti-biotin Antibodies		X†			X	X ^k
Whole-blood sample for T-cell Immune Response Measurement		X†		X	X	
Prior/Concomitant Medication ^l	←		→			
Reactogenicity ^m	←		→			
AEs ⁿ	←		→			
SAEs ⁿ	←		→			
MAAEs including PIMMCs and NOCDs ⁿ	←		→			

Footnotes appear on next page

AE: adverse event; ECG: electrocardiogram; MAAE: medically attended adverse event; NOCD: new-onset chronic disease; PCV13: Prevnar 13; CCI [REDACTED]; PIMMC: potential immune-mediated medical conditions; SAE: serious adverse event; WBC: white blood cell.

† To be performed prior to administration of study vaccine. **Note:** Vital signs will also be performed after the administration of the study vaccine.

‡ Not required if collected at a screening visit, which is ≤ 7days from dosing visit.

§ Visit conducted as a phone call unless anti-biotin antibodies were elevated at day 30 visit.

* If a subject has received any systemically absorbed antibiotics between day 1 and day 30, the visit should take place at least 7 days after the last dose of the antibiotics.

- a. Screening will be completed up to 40 days prior to study immunization. Subjects will be assigned a subject number for use throughout the study at the screening visit via the Interactive Response Technology (IRT) system.
- b. Informed consent must be obtained prior to the performance of any study-related procedure and before randomization.
- c. Subjects will be randomized via the IRT system at the dosing visit.
- d. Medical history will be collected at screening in order to assess Inclusion/Exclusion criteria and will be reconfirmed prior to study immunization.
- e. A physical examination will be performed at the screening visit (days -40 thru -3), prior to study immunization (day 1) and day 30 visits.
- f. Perform tests for Hepatitis B surface antigen (HBsAg), hepatitis A virus antibodies (immunoglobulin M), HCV antibody (anti-HCV) confirmed by reflex testing (HCV-RNA) and HIV antigen/antibody (type 1 and/or type 2) at screening.

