6.2.1.2 Laboratory Values

Laboratory safety assessments will be collected at the screening visit and at study immunization if screening was performed > 7 days from study immunization [day 1]. Assessments will be repeated at follow-up visits on day 7 and day 30. These include the following:

- Hematology (hemoglobin, hematocrit, erythrocytes, leukocytes, differential WBC, platelets),
- Biochemistry (sodium, potassium, calcium, chloride, glucose, total cholesterol, triglycerides, blood urea nitrogen, creatinine, creatine kinase, uric acid, total protein, albumin, c-reactive protein),
- Coagulation profile (prothrombin time, activated partial thromboplastin time, fibrinogen)
- Hepatic profile (alkaline phosphatase, aspartate transaminase, alanine transaminase, γ -glutamyltransferase, total bilirubin, lactate dehydrogenase),
- Urinalysis (using dipstick - protein, glucose, pH, blood, leukocytes, urobilinogen, bilirubin, ketones, nitrite)
- Urine microscopy [optional] (casts, crystals, epithelial cells, leucocytes, erythrocytes, bacteria).
- Pregnancy Testing (Human Chorionic Gonadotropin (hCG))

Laboratory assessments assayed at baseline to determine eligibility are:

- Drug screening (amphetamines, barbiturates, benzodiazepines, cannabinoids and cocaine)
- Virology (Anti-HAV (IgM), HBsAG, Anti-HBc, Anti-HCV, Anti-HIV-1 and 2

Laboratory values collected on Days 7 and 30 will be categorized programmatically using the definitions in Appendix D: Grading Laboratory Abnormalities for Healthy Adult Subjects.

These post vaccination laboratory values are categorized into 4 grads of reactogenicity.

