7.7.3 Visit Windows

The study protocol gives the overall study schedule and the permissible intervals for these visits expressed as the number of days relative to Visit 2.

Analyses will not exclude subject data due to the subject's failure to comply with the visit schedule.

All the assessments will be allocated to CRF visit based on the table below:

CRF visit	Target day	Planned assessment day	Analyzed visit
Visit 1	D-21	D-28 to D-3	Screening
Visit 2	D1	D1	Baseline
Visit 3	D7	D4 to D11	Day 7
Visit 4	D30	D16 to D46	Day 30
Visit 5	D180	D150 to D210	Day 180

The value with the assessment day that is the closest to the defined target day within the windows is used. If two values are equally close, one before and one after the target date, the value with the later date is used in the analysis.

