8 REVISION AND RATIONALE

Version 1 of the SAP has been updated to include planned interim analyses, provide greater details of treatment assignment blinding for study personnel, update the analysis of exploratory endpoints and to correct assorted typographical errors.

Version 2 of the SAP has been updated to

1. Increased screening for Stage 2 to be consistent with the protocol from -28 days to -40 days.
2. Added: “Subjects who are given PPSV23 without previous exposure to PCV13 will not be included in the immunogenicity summaries.” These are subjects in Stage 2, Group 3 who should have received PCV13 before receiving PPSV23.
3. **CCI** [REDACTED]
4. Changed the algorithm for setting the value for LLOQ for the calculation of fold change in response to feedback from the FDA. Values below the LLOQ will be set to $\frac{1}{2}$ LLOQ for calculation of geometric means and set to LLOQ for calculation of fold changes.
5. **CCI** [REDACTED]
6. **CCI** [REDACTED]
7. Added a CMH rank test to examine the difference between ASP3772 and PCV13 in the number of reactogenicity reactions. Added a CMH statistics with scores=modridit to compare the severity for each type of reaction between each dose of ASP3772 and PCV13 after assigning an increasing score to each severity.
8. Added details for determining systemic reactogenicity events during the 1st hour post vaccination.

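### Two SAP window tables still start at Day -28 although Stage 2 screening may start at Day -40, leaving 12 permitted screening days in no analysis window

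*SAP*

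**What the plan says.** **Screening period.** For Stage 1 the SAP schedule (section 2, Table 1) says "Screening will be completed up to 28 days prior to study immunization". For Stage 2, Groups 2 and 3 (Tables 2 and 3), it says "Screening will be completed up to 40 days prior to study immunization". The protocol's schedules give the same limits. SAP section 8 records the change: "Increased screening for Stage 2 to be consistent with the protocol from -28 days to -40 days".

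**Laboratory baseline window.** SAP 7.7.1 defines the baseline as "Last non-missing value between -28 and 1 (inclusive"), with no separate entry for Stage 2. SAP 7.5.3 defines the laboratory baseline differently, as the last pre-vaccination measurement with no day limit. Protocol section 7 has a similar general definition.

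**Visit allocation.** SAP 7.7.3 states: "All the assessments will be allocated to CRF visit based on the table below". That table has one Visit 1 row, D-28 to D-3, for both stages. The selection rule follows: "The value with the assessment day that is the closest to the defined target day within the windows is used".

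**What is repeated on Day 1.** SAP 6.2.1.2 requires laboratory tests "at study immunization if screening was performed > 7 days from study immunization [day 1"]. Vital signs and an ECG are also scheduled before dosing on Day 1. Height, body weight and virology are scheduled at screening only. On ECGs, Protocol 5.4.7 says: "The interpretation of the ECG from screening will be the baseline to which post-study vaccine dosing ECGs will be compared".

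**The concern.** The schedule and the analysis windows are both current text, and they disagree for Stage 2. A subject screened on Day -35 has followed the protocol, yet no row of 7.7.3 contains that day and 7.7.1 does not reach it. The revision log is not itself the contradiction. It shows only that the move to Day -40 was deliberate, so the two remaining -28 limits look like entries that were overlooked.

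Two things are at stake. First, items taken only at screening, together with the screening ECG, would have no analysis visit if the table were programmed as written. Second, 7.7.1 and 7.5.3 give different answers for an early-screened subject whose Day 1 laboratory sample is missing or unusable: one rejects the screening value and the other accepts it. Either case leaves the programmer to make an unplanned choice.

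**Working it through.** The plan states no figure to reproduce. The check counts days and sets each permitted screening day against the windows.

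**Inputs**
- Permitted Stage 2 screening: Day -40 to -3 (SAP section 2, Tables 2 and 3)
- Permitted Stage 1 screening: Day -28 to -3 (SAP section 2, Table 1)
- Visit 1 window: D-28 to D-3; the other rows are D1, D4 to D11, D16 to D46 and D150 to D210 (SAP 7.7.3)
- Laboratory baseline window: Day -28 to 1 (SAP 7.7.1)
- Planned Stage 2 subjects: 3 × (99 + 33) + 99 = 396 + 99 = 495

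**Day count**
- Permitted Stage 2 days: 40 - 3 + 1 = 38
- Covered by Visit 1: 28 - 3 + 1 = 26
- In no 7.7.3 row: 38 - 26 = 12 (Day -40 to -29), and 12/38 = 31.6%
- Outside the 7.7.1 baseline window: the same 12 days
- Stage 1: 26 permitted days, 0 uncovered

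**Comparison with the other rows of 7.7.3**

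| Visit | Protocol window | SAP window |
|---|---|---|
| Day 7 | D7 to D8 | D4 to D11 |
| Day 30 | D28 to D32 | D16 to D46 |
| Day 180 | D166 to D194 | D150 to D210 |
| Screening, Stage 2 | D-40 to D-3 | D-28 to D-3 |

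The follow-up windows are all wider than the protocol's. Stage 2 screening is the only row that is narrower.

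**Which data are exposed on the 12 days**
- Laboratory tests: all 12 days are more than 7 days before dosing, so a Day 1 sample is required in every case. The screening value matters only if that sample is missing or unusable.
- Vital signs: a pre-dose Day 1 reading is scheduled.
- Height, body weight, virology: screening only, so there is no Day 1 value.
- ECG: the screening tracing is the protocol's baseline. A Day 1 tracing also exists, but 5.4.7 does not name it as the baseline.
- Immunogenicity and anti-biotin: the baseline is Day 1 only (SAP 7.7.2), so these are unaffected.

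**Number of subjects.** The documents give no distribution of screening days. As assumptions only, applied to 495:

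| Assumed share screened on Day -40 to -29 | Subjects |
|---|---|
| 5% | 0.05 × 495 ≈ 25 |
| 10% | 0.10 × 495 ≈ 50 |
| 20% | 0.20 × 495 = 99 |
| 31.6% (even spread over the 38 days) | 12/38 × 495 ≈ 156 |

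These count subjects screened early, not subjects who lose a value.

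**The case against.** The strongest case against is that almost nothing depends on the window.

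- **Laboratory data.** The Day 1 repeat puts a scheduled value inside the 7.7.1 window for every early-screened subject. This stands, and leaves only the missing or unusable sample.
- **Height, weight and BMI.** A reader might infer that these are missing for early-screened subjects. The documents do not support that. SAP 7.2.3 summarises them at study entry and cites no window. Moreover, 7.7.3 labels only D1 as Baseline, so a strict reading would leave nobody in either stage with a baseline height or weight. The table is evidently not meant to control that summary. The narrower point remains: a Day -10 height is assigned to Screening, and a Day -35 height is assigned to nothing.
- **ECG.** A reader might also infer that the ECG baseline is lost. SAP 7.5.5 only lists ECGs, and the comparison with screening is the investigator's clinical reading, which needs no SAP window.
- **Virology.** It serves eligibility, and no analysis of it is planned.
- **Intent.** SAP 7.7.3 says subjects who fail to comply with the visit schedule will not have data excluded for that reason. It would be odd to keep those data and discard data from permitted visits. This is a fair guide to intent, but the sentence covers non-compliance, and a subject screened on Day -35 has complied.

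It is also tempting to say that early-screened subjects cluster around the cohort review pauses. The protocol's Attachment 1 gives the timing of cohort data reviews as the reason for extending screening, but gives no distribution of screening days. Clustering is conjecture, and it would contradict the even spread behind the 31.6% share.

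**Conclusion.** The inconsistency is real and sits in current text: two SAP tables were not updated when Stage 2 screening was extended, and 12 of 38 permitted days (31.6%) fall in no window. Applied literally, screening-only items and the screening ECG from those days have no analysis visit, and 7.7.1 conflicts with 7.5.3 when the Day 1 laboratory sample is missing or unusable.

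The consequence is minor. No immunogenicity result changes, and no safety comparison is shown to change. The number screened this early is unknown. The range of about 25 to 156 subjects rests wholly on assumed shares of 5% to 31.6% of 495, and many or most of those subjects would keep every value that the planned summaries use. This is a correction worth making before programming, not a threat to the study's conclusions.

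**What to change.** - SAP 7.7.1, Baseline row: set the lower bound to Day -40 for Stage 2 and keep Day -28 for Stage 1.
- SAP 7.7.3, Visit 1 row: split by stage, D-28 to D-3 for Stage 1 and D-40 to D-3 for Stage 2.
- Align 7.7.1 with 7.5.3, so that the laboratory baseline is the last value before vaccination under both sections.

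Uncovered Stage 2 screening days then fall from 12 of 38 to 0 of 38, and Stage 1 stays at 0 of 26. The cost is two table entries and one sentence in the SAP. Design, sample size and data collection do not change, and there is no analytical downside.

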7.7.2 Blood Sampling for Immunogenicity, Anti-biotin and T-cell Immune Response Analysis Windows

Analysis Visits	Scheduled Day in Protocol	Analysis Windows (day)
Baseline	Day 1	Last non-missing value on day 1 prior to immunization dosing
Visit 3	Day 7	Closest non-missing post immunization value to study day 7
Visit 4	Day 30	Closest non-missing post immunization value to study day 30
Visit 5	Day 180	Closest non-missing post immunization value to study day 180

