5.3.1 Immunological Response

Considering its mechanism of action, ASP3772 is expected to induce the immune response to pneumococcal PS and carrier proteins, the antigens present in ASP3772. Blood samples to assess immunogenicity will be collected as indicated in the Schedule of Assessments [Table 1, Table 2 and Table 3]. Immunogenicity assessments will be performed from blood samples collected at the dosing visit (day 1) prior to study immunization and at the 7-day and 30-day follow-up visits. Immunogenicity data will be provided to the investigative site when available.

Immunogenicity of ASP3772 will be evaluated by measuring serotype-specific anticapsular IgG antibody concentrations by multiplex direct Luminex immunoassays and OPA titers against the 24 vaccine serotypes in serum samples. OPA measures the functional killing activity of antibodies against the pneumococcal serotypes. In addition, pneumococcal carrier protein (SP1500+0785)-specific immune response will be assessed by measuring specific IgG in serum and activity against non-vaccine serotypes. Thelper 17 cells (Th17) response to SP1500+0785 will be evaluated by measuring interleukin (IL)-17.

blood mononuclear cells (PBMCs) as exploratory assessments.

Details on sampling, processing and storage will be described in the laboratory manual. Samples will be shipped on dry ice to a designated contract research organization (CRO) for the analyses.

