6 DISCONTINUATION

6.1 Discontinuation of Individual Subject(s) From Study

Individual subjects will be discontinued from the study if:

- Subject is lost-to-follow-up despite reasonable efforts by the investigator to locate the subject.
- Subject can voluntarily withdraw from the study at any time for any reason.

The reason for discontinuation from study must be documented in the subject's medical records.

Any subject who has received immunization, but withdraws consent, will be asked to complete the day 30 study assessments at the time of their withdrawal if possible.

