Stage 2 of the study is a dose-finding (sequentially higher doses), active-controlled, observer-blinded study with a 3:1 randomization (ASP3772:PCV13) in elderly subjects 65 to 85 years of age (Group 2). For Stage 2, Group 2 subjects the vaccine administrator will differ from the person evaluating reactogenicity to remove reporting bias for these events. Treatment assignment will also be unknown to the blinded study team.

After screening, PCV13 naïve subjects will be randomized within each cohort to receive ASP3772 or PCV13. Subjects randomized to ASP3772 will receive a single dose of ASP3772 administered as a 0.5 mL intramuscular (IM) injection on day 1, at 1 of 3 dose levels: 1, 2 or 5 µg of ASP3772 for Cohorts 4, 5 and 6, respectively. The subjects randomized to PCV13 will receive a single injection of the standard dose of PCV13.

Stage 2 will commence after the DEC has evaluated safety (including reactogenicity) data through 30 days from all cohorts in Stage 1. Dose escalation to Cohort 5 (intermediate dose, 2 µg) in Stage 2 will commence once the DEC has evaluated Stage 2 Cohort 4 (1 µg) safety (including reactogenicity) and tolerability through 7 days postimmunization. Dose escalation into Cohort 6 (high dose, 5 µg) in Stage 2 will commence once the DEC has evaluated Stage 2 Cohort 5. The DEC will review the data for each cohort in Stage 2, Group 2 in a blinded manner. The DEC Charter will provide details for revealing the treatment assignment for individual subjects to DEC members, if necessary. Randomization for Stage 2 subjects will be stratified by age (65 to 74 years of age and 75 to 85 years of age) to ensure there is a balanced number of subjects within each age cohort immunized with either ASP3772 or PCV13.

Safety and tolerability assessments including adverse events (AEs) will continue through 30 days postimmunization. Safety assessments for SAEs and MAAEs including PIMMCs and NOCDs will continue through day 180 postimmunization. Data will be collected in an observer-blinded manner (vaccine recipients and the site staff who are responsible for evaluation of any study endpoint will be unaware of which vaccine the subject received).

Serum samples to measure IgG and OPA will be collected prior to study vaccination on day 1 and postimmunization on day 30. The primary immunogenicity evaluation for dose finding is 30 days following the initial immunization.

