7.4.2 Analysis of Non-Vaccine-Type (NVT) Pneumococcal Immunogenicity

In both Stage 1 Group 1 and Stage 2 Group 2, blood draws to determine SP1500+0785 levels (ng/mL) will be collected for subjects given either ASP3772 or PCV13. Levels of TH17 will be determined using an ELISpot assay and IL17 will be measured using a standard MSD ELISA. Levels of the following cytokines will also be assayed: IL-17, IL-22, CCI [REDACTED]. Summaries of the levels at baseline, Day 7 and Day 30 will be provided. The fold increase relative to baseline at Days 7 and 30 will also be summarized. Paired comparisons between each of the ASP3772 dose levels and PCV13 will be completed using a Wilcoxon Test. These comparisons will be made for subjects in Stage 1, Group 1 and separately for subjects in Stage 2, Group 2.

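### SAP 7.7.1 and 7.7.2 pick the closest post-dose value with no day limits, SAP 7.7.3 sets limits for all assessments, and the plan does not say which rule governs

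*SAP*

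**What the plan says.** - **SAP 7.7.1 and 7.7.2 (data-specific tables).** For clinical laboratory data, and for immunogenicity, anti-biotin and T-cell samples, the Day 30 row reads "Closest non-missing post immunization value to study day 30". The Day 7 rows, and the Day 180 row in 7.7.2, follow the same pattern. No post-dose row gives an earliest or latest day.
- **SAP 7.7.3 (general table).** "All the assessments will be allocated to CRF visit based on the table below", with Day 7 as D4-D11, Day 30 as D16-D46 and Day 180 as D150-D210. The selection rule is bounded: "The value with the assessment day that is the closest to the defined target day within the windows is used". The same subsection also states: "Analyses will not exclude subject data due to the subject's failure to comply with the visit schedule".
- **Sampling days.** For IgG and OPA in Stage 2, SAP 3.2 says "Serum samples to measure IgG and OPA will be collected prior to study vaccination on day 1 and postimmunization on day 30", and it gives the same days for Stage 1. Laboratory tests and whole-blood T-cell samples are also taken on Day 7 (SAP Tables 1 and 2). SAP 7.4.2 says of the non-vaccine-type and cytokine measures: "Summaries of the levels at baseline, Day 7 and Day 30 will be provided". Anti-biotin is sampled on Day 180 only in subjects positive at Day 30 (SAP 6.5).
- **Withdrawal.** Under Protocol 6.1, an immunized subject who withdraws consent "will be asked to complete the day 30 study assessments at the time of their withdrawal if possible".
- **Analysis sets.** The full analysis set (FAS), used for the primary immunogenicity analyses, requires only one post-immunization measurement and has no draw-time limit (SAP 5.1).

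**The concern.** The two sets of rules give different analysis datasets, and the SAP does not rank them. A programmer could reasonably let the data-specific tables override the general one, because 7.7.1 already departs from it at baseline: the laboratory baseline may come from Day -28 to Day 1, whereas 7.7.3 maps Baseline to D1 only.

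On that reading three things go wrong:

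1. One laboratory or T-cell sample can fill both the Day 7 and the Day 30 row. In effect this is imputation, which Protocol 7.10 rules out as a general principle.
2. A subject negative for anti-biotin at Day 30, and so not resampled, receives the Day 30 result as a Day 180 result. This needs no dropout and no protocol deviation.
3. IgG/OPA serum drawn at an early withdrawal enters the Day 30 geometric mean titer or concentration and the GMFR in the FAS.

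The third matters most for the study's purpose, since Stage 2 responses are to inform the phase 3 dose and sample size (SAP 4).

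**Working it through.** The plan states no result that can be reproduced here. The only figures that bear on the point are the 7.7.3 windows, and the check is to apply both rules to the same sampling days.

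**Step 1. Which value becomes Day 30?** Inputs: the row wording in 7.7.1/7.7.2, and the 7.7.3 window of D16-D46 (30 - 16 = 14 days before target, 46 - 30 = 16 days after).

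| Post-dose sample(s) available | 7.7.1/7.7.2 read alone | 7.7.3 |
|---|---|---|
| Day 7 only (laboratory, T-cell) | Day 7 value, which also fills Day 7 | missing |
| Withdrawal draw on Day 3, 8, 10 or 14 | that draw | missing |
| Withdrawal draw on Day 16 or 20 | that draw | that draw |
| Day 50 only | Day 50 value | missing |
| Day 7 and Day 30 | Day 30 value | Day 30 value |

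Read alone, the 7.7.2 rows also let a lone Day 30 sample fill Day 7 and Day 180. Under 7.7.3 the windows do not overlap, so one sample cannot serve two visits. Days 12-15 and 47-149 belong to no post-dose visit.

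**Step 2. Which data can be affected?**

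- *Laboratory and T-cell:* sampled on Day 7 and Day 30, so either can stand in for the other.
- *Anti-biotin:* the Day 180 row in 7.7.2 reaches back to Day 30 in every subject who was not resampled.
- *IgG and OPA:* Protocol 5.3.1 mentions samples "at the 7-day and 30-day follow-up visits" without separating the assays, but it refers to the schedules. Those schedules, Protocol Appendix 12.5 and SAP 3.2 place this serum on Day 1 and Day 30 only. Exposure is therefore limited to withdrawal or off-schedule draws.

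**Step 3. Illustrative size for IgG/OPA.** Let the true GMFR be R, and let a share w of subjects contribute an early draw with no rise (fold rise 1). Then

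ln(observed GMFR) = (1 - w) ln R + w ln 1, so observed / true = R^(-w).

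Neither R nor w is in the documents; both are assumptions.

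- One subject in 99 (a Stage 2 dose group): 4^(-1/99) = 0.986 and 16^(-1/99) = 0.972, which is 1.4% to 2.8% too low.
- One subject in 30 (a Stage 1 dose group): 4^(-1/30) = 0.955 and 16^(-1/30) = 0.912, which is 4.5% to 8.8% too low.
- A share of 5%, or 0.05 × 99 ≈ 5 subjects: 4^(-0.05) = 0.933 and 16^(-0.05) = 0.871, which is 6.7% to 12.9% too low.

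**Step 4. Compare with sampling error.** SAP Appendix A puts the lower 95% limit at GM / GSD^(t/√n). With n = 99, t = 1.984 and an assumed geometric SD of 3 to 5, the exponent is 1.984/9.950 = 0.199. The lower limit is then 3^(-0.199) = 0.80 to 5^(-0.199) = 0.73 of the estimate, or about 20% to 27% below it. One misassigned draw is small against that.

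**The case against.** The strongest reply is that the bounds already exist. SAP 7.7.3 covers all assessments, and the rows in 7.7.1 and 7.7.2 can be read as saying which value to pick while 7.7.3 says where it may come from. On that reading a Day 8 serum sample falls in D4-D11 and is never a Day 30 value. This reading is tenable, and nothing in the SAP says that the specific tables override it. Nothing says the opposite either. The differing laboratory baseline and the sentence on not excluding off-schedule data both pull towards the unbounded reading.

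For IgG/OPA the route is also narrow. It needs a subject who withdraws consent before Day 16 of a single-dose study and still agrees to a blood draw, which Protocol 6.1 asks for only where possible. Subjects lost to follow-up give no sample. The rule applies to every arm, so ASP3772/PCV13 ratios for shared serotypes move little if early withdrawal is balanced. All of this stands, and it keeps the likely effect small.

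The per-protocol set (PPS) gives only partial cover. SAP 7.2.1 describes it as Day 30 draws between Day 30 and Day 44, which would exclude early draws. SAP 5.2 excludes only late draws, and the PPS is supportive and produced if needed.

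A reader might infer that the plan sets no bounds at all, or that Day 7 serum will be analysed as Day 30 IgG/OPA. The documents support neither: 7.7.3 does set bounds, and no Day 7 serum is scheduled for those assays.

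**Conclusion.** The defect is an unresolved conflict between an unbounded and a bounded window rule, with no stated precedence. It should be settled before programming, because two competent programmers could produce different datasets. If 7.7.3 governs, no sample before Day 16 becomes a Day 30 value. If the data-specific tables govern, laboratory, T-cell and anti-biotin values can be reported under the wrong visit, and early-withdrawal IgG/OPA serum counts as Day 30.

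The IgG/OPA effect is probably small: about 1.4% to 2.8% on the GMFR for one early draw among 99, assuming a true fold rise of 4 to 16 and no rise at all in that subject, which is close to a worst case. A reader might take the 12.9% in the working as the expected bias. It is not: it needs about five of 99 subjects to withdraw early, all to be bled, none to show a rise, and a true fold rise of 16. The documents give no early-withdrawal rate or fold rise from which to judge that likely. These are also secondary endpoints.

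**What to change.** In the SAP:

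1. State in 7.7.1 and 7.7.2 that the 7.7.3 bounds (D4-D11, D16-D46, D150-D210) govern the post-dose rows. Keep the data-specific baseline rules.
2. State that a value outside the window is missing for that visit but still listed, and that one sample serves only one analysis visit.
3. Reword the 7.7.3 sentence on not excluding data for visit non-compliance so that it agrees. For example, no subject leaves an analysis set because of timing, and off-schedule values are used only within a window.
4. Say how withdrawal draws on Days 16-27 are handled. They fall inside D16-D46 but before the protocol's Day 30 (±2) visit, so the bounds alone do not settle them. One option is to keep them in the main analysis and add a sensitivity analysis without them.

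The cost is a few sentences of SAP text, matching programming specifications and possibly one sensitivity table. The downside is that a few out-of-window values, including any on Days 12-15 or 47-149, become missing for the visit.
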